4.1.3. Study Day

The *study day* describes the relative day of an observation starting with the reference date designated as Study Day 1. In this study, the treatment start date is the reference date.

For Period 1 and entire study period, the study day will be calculated as:

Study Day = Date - Period 1 Treatment Start Date + 1

For subjects who entered Period 2 (i.e., got randomized), their *Period 2 study day* will be calculated as:

Period 2 Study Day = Date – Period 2 Treatment Start Date + 1

4.1.4. Analysis Visit and Analysis Window

Analysis visit is a timing variable to be used for analyses involving visits. For each analysis visit, an analysis window is set up to determine the analysis visit a measurement should be mapped to.

The following *analysis windows* will be applied to minimize the amount of missing data for analysis purposes:

Analysis Visit (Target Study Day)	Protocol Visit Window	Analysis Window
Period 1	(Refers to Study Day for the entire study period)	(Refers to Period 1 Study Day)
Baseline (Day 1)	[1, 1]	[-, 1]
Month 3 (Day 90)	[83, 97]	[2, 135]
Month 6 (Day 180)	[173, 187]	[136, 225]
Month 9 (Day 270)	[263, 277]	[226, 315]
Month 12 (Day 360)	[353, 367]	[316, ET in Period 1 or Randomization First Dose Date in Period 2]
Period 2	(Refers to Study Day for the entire study period)	(Refers to Period 2 Study Day)
Month 12 (Day 360)	[353, 367]	[-, 1(First Dose Date in Period 2)]
Month 15 (Day 450)	[443, 457]	[2, 135]
Month 18 (Day 540)	[533, 547]	[136, 225]
Month 21 (Day 630)	[623, 637]	[226, 315]
Month 24 (Day 720)	[713, 727]	[316, 405]
Month 27 (Day 810)	[803, 817]	[406, 495]
Month 30 (Day 900)	[893, 907]	[496, 585]
Month 33 (Day 990)	[983, 997]	[586, 675]
Month 36 (Day 1080)	[1073, 1087]	[676, 765]

ET= Early Termination.

The analysis visit of a measurement will be determined based on the study day of the measurement and specified analysis window, and is not necessarily the same with the protocol study visit where the measurement was collected. For analyses involving post-baseline visits, if there are two or more measurements that fall into the same analysis window of a post-baseline visit, then the measurement closest to the target assessment day will be selected for that visit. In the case that two measurements are closest and equidistant to the target assessment day, i.e., one is before and one is after the target assessment day, the latter one will be selected for that visit.

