# 10.1.5. Month 18 (D540) (±7 days), Month 24 (D720) (±7 days), and Month 30 (D900) (±7 days)

- Record of concomitant ocular and systemic medications [other than artificial tear (AT) usage]
- Urine pregnancy test (women of childbearing potential only)
- Record adverse events (AEs)
- Assessment of Artificial tears use by questioning the patient
- Symptoms evaluation by completing SANDE questionnaire
- Symptoms evaluation by completing the 0-4 point scale
- Quality of life questionnaires (DEQS)
- BCDVA
- Slit lamp examination
- TBUT
- Corneal and conjunctival fluorescein staining (modified Oxford scale)
- Schirmer test (without anaesthesia) ONLY at Month 24 (D720)
- IOP ONLY at Month 24 (D720)
- Collection of used/not used study medication containers and unpreserved artificial tear bottles
- Assessment of compliance to study medication
- Dispensation of study medication and unpreserved artificial tears for a 3-month period
- Patients will be scheduled to return to the clinic in 3 months (90 days  $\pm$  7 days) for the next study visit

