4.1.2. Treatment Start Date and End Date

The treatment start and end dates for each treatment period and the study are defined as follows:

Treatment Period	Treatment Start Date	Treatment End Date
Open-Label Treatment Period (Period 1)	The date of the first dose of the open-label IKERVIS treatment (or Day 1 date)	 The date of the last dose of the open-label IKERVIS treatment The date of the day before the Month 12 Visit will be considered the Period 1 treatment end date for subjects who completed Period 1 treatment. The date of the day before the Exit Visit will be used for subjects who prematurely discontinued from the study. If the Exit Visit date of a non-completer is not available, then the day before the last available visit date will be considered the treatment end date.
Double-Masked Treatment Period (Period 2)	The date of the first dose of the double-masked study treatment (or Month 12 Visit date)	 The date of the last dose of the double-masked study treatment The date of the day before the Month 36 Visit will be considered the Period 2 treatment end date for subjects who completed the study. The date of the day before the Exit Visit will be used for subjects who prematurely discontinued from the study. If the Exit Visit date of a non-completer is not available, then the day before the last available visit date will be considered the treatment end date.

For each treatment period, the treatment end date will be set to missing if the treatment start date is missing.

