7.6. Treatment Compliance

Compliance to the study medication use is tracked on the Compliance eCRF as the number of single dose medication containers not used and returned.

Due to the irregularities in returning containers caused by COVID-19 situation, the treatment compliance will be assessed by study period rather than by intervals based on scheduled visits as specified in the protocol. Since some visits, for example, happened remotely, dispensing or returning of study drug could not happen on a scheduled time. Compliance rate will be calculated for Period 1, and Period 2, respectively.

For a given analysis period, compliance rate will be calculated using the following formula, which assumes that the unreturned containers are not used:

Treatment Compliance Rate (%) in Period x

 $= \frac{\text{No. of dispensed containers-(No. of returned unused containers + No. of unreturned containers)}}{\text{Duration of Period x}} \times 100$

where the Duration of Period x is the number of days subjects should have administered study medication in the analysis period, calculated as

Duration of Period x =end date of study drug in Period x -start date of study drug in Period x.

Compliance rate of \geq 80% will be treated as compliant. Compliance will be summarized continuously and categorically (compliant and non-compliant) for FAS subjects for Period 1 and Period 2 separately. Period 2 summaries will be performed by planned treatment and overall.

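### SAP 4.1.4 has no rule for data after Period 2 day 765, so a late visit or a late first masked dose can drop, mislabel or empty Month 36

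*SAP*

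**What the plan says.** SAP 4.1.4 sets up analysis windows that "will be applied to minimize the amount of missing data for analysis purposes". A measurement is assigned by its study day, and the SAP says openly that the result may differ from the protocol visit at which it was collected. If two or more measurements fall in one window, "the measurement closest to the target assessment day will be selected for that visit"; if two are equally distant, the later one is used.

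The Period 2 analysis windows carry the note "Refers to Period 2 Study Day", and SAP 4.1.3 defines "Period 2 Study Day = Date – Period 2 Treatment Start Date + 1". Day 1 is the first masked dose, or the Month 12 visit date (SAP 4.1.2). The Month 36 window is days 676 to 765. The Period 1 window for Month 12, by contrast, stays open until early termination or the first Period 2 dose.

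The targets beside the Period 2 windows are Day 450 to Day 1080. These are whole-study days, like the adjoining protocol-window column, which is headed "Refers to Study Day for the entire study period".

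The protocol gives sites two anchors. Table 3 and the headings of sections 10.1.2 to 10.1.6 fix visits at absolute days, up to D1080 ± 7. The last bullet of sections 10.1.1 to 10.1.5 instead counts from the current visit: "Patients will be scheduled to return to the clinic in 3 months", with 90 ± 7 days in brackets. Neither document says which prevails after a late visit.

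**The concern.** By-visit summaries, the Period 2 MMRM (SAP 8.2.1) and the lagged CFS–SANDE correlations (SAP 8.1.1) are all organised by visit and so depend on this mapping. A subject who attends all eight Period 2 visits can still have no Month 36 value, or a Month 33 value reported as Month 36, because of where day counts fall against the windows. Measures taken at only a few visits are hit hardest. That works against the section's own aim of limiting missing data.

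**Working it through.** **Inputs.** Period 2 windows, targets and selection rule: SAP 4.1.4. Day formula: SAP 4.1.3. Booking interval and fixed days: Protocol 10.1.1 to 10.1.6 and Table 3. The delay lengths below are assumptions chosen to find the thresholds.

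**The plan's own limits.** The upper limit of the k-th Period 2 window is 90k + 45. For k = 1 to 8 this gives 135, 225, 315, 405, 495, 585, 675 and 765, matching all eight rows.

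**Case A: each visit booked 90 days after the last.** With masked dosing from the Month 12 visit date, visit k falls on day 1 + 90k. After one delay of d days, Month 36 falls on 721 + d. That exceeds 765 when d ≥ 45. If dosing starts the next day, it falls on 720 + d and the threshold is 46. A delay before Month 12 does not count here, because the Period 2 clock restarts there.

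A 45-day delay at Month 24:

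| Visit attended | Period 2 day | Analysis visit |
|---|---|---|
| Month 21 | 271 | Month 21 |
| Month 24 | 361 + 45 = 406 | Month 27 |
| Month 27 | 496 | Month 30 |
| Month 30 | 586 | Month 33 |
| Month 33 | 676 | Month 36 |
| Month 36 | 766 | none |

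With a 44-day delay every label is right (Month 36 on day 765). If only Month 36 is 45 days late, it is dropped and nothing else moves.

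**Case B: fixed days kept, Month 12 and first masked dose on day 360.** A 45-day delay at Month 24 moves that visit alone to day 406, in the Month 27 window. The on-time Month 27 visit (day 451) is closer to target and is used, so the Month 24 cell is empty. Month 36 stays on day 721 and is kept. With every visit inside its ± 7 days and dosing from the Month 12 visit, Month 36 lies between 1073 − 367 + 1 = 707 and 1087 − 353 + 1 = 735, well inside its window.

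**Case C: fixed days kept, first masked dose late.** Period 2 day = D-day − first-dose day + 1. With the first dose on study day 406:

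| Visit attended | Period 2 day | Analysis visit |
|---|---|---|
| Month 15 (D450) | 45 | Month 15 |
| Month 18 (D540) | 135 | Month 15 |
| Month 24 (D720) | 315 | Month 21 |
| Month 33 (D990) | 585 | Month 30 |
| Month 36 (D1080) | 675 | Month 33 |

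Month 36 is empty. If the final visit is on D1073, this begins with a first dose on day 399: 1073 − 399 + 1 = 675.

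**Sparse measures.** In the Case A table, Schirmer's Month 24 value is labelled Month 27 and its Month 36 value is lost. In Case C the two values land at Months 21 and 33. Either way neither planned visit has data. In Case A with a slip by Month 18, DEQS moves to Months 21, 27 and 33, and its Month 36 value is lost.

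**Target clock.** On the Period 2 clock, Day 1080 is 1080 − first-dose day + 1. For a first dose on days 353 to 367 this is 728 to 714, inside the window. It leaves its own window only after a long delay: with a first dose on day 410, the Month 18 target is 540 − 410 + 1 = 131, below 136.

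**Size if Month 36 values are lost (assumed fractions).** The stated 80% power for a CFS difference of 0.4 (SD 1.10; 147 versus 98) reproduces as 79.6%. Losing 5%, 10% or 20% of each arm gives 77.6%, 75.3% or 70.3%.

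**The case against.** The best defence is that mapping by actual day is deliberate and disclosed, and that the fixed days with ± 7 appear throughout: Protocol Table 3, the visit headings, SAP Table 1 and the window table itself. Protocol 10.1.7 also returns a patient to the next planned visit after an unscheduled one, which points to a fixed calendar. On that calendar one late visit does not cascade. This stands, and it makes the relabelling conditional on booking from the last visit. It does not supply a rule after day 765, and it does not protect Case C.

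Several stronger readings are tempting but not supported:

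- **Any 45-day delay loses Month 36.** Case B shows otherwise.
- **Steady gaps of 96 or 97 days are permitted and also lose Month 36.** They satisfy the booking bullet (Month 36 on day 769 or 777) but breach the fixed days. Even from Month 12 on D353, Month 21 falls on D641 or D644, past D637.
- **The whole-study targets cause the relabelling or the drop.** They do not. They matter only when two measurements share a window. Case C arises because visits are fixed on one clock and windows run on the other.
- **The SAP documents long delays.** SAP 7.6 says "Since some visits, for example, happened remotely, dispensing or returning of study drug could not happen on a scheduled time", which concerns container returns and gives no delay lengths. A 135-day interval would also outlast one 110-container box (Protocol 9.2) unless more were dispensed.
- **Month 36 is the only endpoint visit.** The MMRM reports every visit and the correlations span many visit pairs.
- **Failing to prefer scheduled over unscheduled visits is an error.** Closest-to-target with a tie-break is a complete rule, and the preference is a matter of choice.

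It is also fair to say that in the Case A table nobody was seen in days 316 to 405, so an empty Month 24 describes what happened. That does not excuse discarding an attended Month 36 visit.

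**Conclusion.** The gap is real and conditional. Without any assumption about booking, a Month 36 assessment after Period 2 day 765 belongs to no visit. Booking from the last visit adds a one-label shift from a delay of 45 days (46 with next-day dosing). Fixed-day booking empties Month 36 when the first masked dose is on study day 406 (final visit on D1080) or 399 (final visit on D1073), which is 39 or 32 days past the protocol's Month 12 window.

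The CFS, SANDE and TBUT analyses by visit are exposed, Schirmer most of all. Complication rates based on adverse events do not use these windows. The number of subjects affected cannot be derived from the documents. At the assumed losses of 5% to 20%, the power cost at Month 36 is about 2 to 9 percentage points. The correction is cheap enough to make regardless.

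**What to change.** In SAP 4.1.4:

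- **(a)** Leave the Month 36 window open through the last Period 2 assessment, and say that this includes the Month 36 visit itself. Wording such as the end of Period 2 would not do: the only Period 2 end date in SAP 4.1.2 is the treatment end date, which for completers is the day before that visit.
- **(b)** State Period 2 targets on the Period 2 clock: about day 91, 181 and so on to 721.
- **(c)** Keep the nominal eCRF label for completed scheduled visits, at minimum so that the nominal Month 36 assessment supplies Month 36. Use the day windows for unscheduled and early-termination data.

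Part (c) is essential. With (a) and (b) alone, a 46-day slip in Case A puts Months 33 and 36 on days 677 and 767. These are 44 and 46 days from 721, so the Month 33 value still wins. In Case C, day 675 stays in the Month 33 window. With nominal labels, all eight visits keep their place in the 45-day example.

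The protocol's fixed days ± 7 and its 90 ± 7 days from the previous visit must be reconciled, with a clarification to sites.

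The cost is SAP wording, one programming rule and that clarification. The small downside is that some values labelled Month 36 will lie more than 45 days from target.

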4.1.5. Extent of Exposure

The *extent of exposure* (*days*) to study medication will be assessed by duration of treatment exposure.

• For subjects who only received study treatment in Period 1 and exited the study, their duration of treatment exposure will be derived as:

Duration of IKERVIS exposure =

(Period 1 Treatment end date – Period 1 Treatment start date) + 1

• For subjects who entered Period 2 and received IKERVIS treatment, their duration of treatment exposure will be derived as:

Duration of IKERVIS exposure =

(Period 2 Treatment end date – Period 1 Treatment start date) + 1

• For subjects who entered Period 2 and actually received the Vehicle treatment, their duration of treatment exposure will be derived as:

Duration of IKERVIS exposure =

(Period 1 Treatment end date – Period 1 Treatment start date) + 1

Duration of Vehicle exposure =

(Period 2 Treatment end date – Period 2 Treatment start date) + 1

4.2. Endpoint-Related Definitions

4.2.1. Study Eye and Fellow Eye

The study eye will be the eye that fulfils all the criteria listed under the inclusion criteria #5. If both eyes are eligible, the eye with the highest baseline CFS score will be chosen. If not discriminant, the eye with the lowest Schirmer test value will be chosen. If not discriminant, the right eye will be chosen as the study eye. The other eye will be the non-study eye, or fellow eye.

4.2.2. Baseline Score

The *baseline score* is the observed measurement at Baseline (Day 1).

In addition, for subjects who got randomized in Period 2, the observed measurements made at Month 12 Visit will be used as baseline scores for Period 2. If a Month 12 measurement is

missing, the last observed measurement or derived score prior to the first dose of the Period 2 double-masked study treatment will be used to impute the baseline score for Period 2.

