**AND** 

• Schirmer test without anaesthesia scored <10 mm/5min in the same eye at Baseline Visit,

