^c Symptom of dry eye will be evaluated at each study visit by completing SANDE questionnaire and 5 symptoms using a 0-4 point scale.

^d QoL and BCDVA will NOT be assessed and slit lamp examination will not be performed at Month 3 and 9. TBUT and corneal and conjunctival fluorescein staining which will be performed at each visit.

^e Schirmer test and IOP will NOT be performed at Month 18 and 30 visits.

f Record AEs if the unscheduled visit is after the first study drug administration.

g Dispensation of study medication and/or unpreserved artificial tears if necessary.

h Randomisation of markedly improved subjects at Month 12 visit.

¹ Dispensation of masked study medication (IKERVIS® or Vehicle).

4. **DEFINITIONS**

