4.2.3. Change from a Reference Point

For Period 1 and Entire Study analyses, the change from baseline at a post-baseline visit will be derived as:

```
Change = (Score at the Post-Baseline Visit) – (Baseline Score)
```

For Period 2 analyses, change from Month 12 will be the change used in the analyses.

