4.4.2. Other Safety Measures

Table 2 lists the safety measures to be evaluated for this study.

Table 2. Safety Assessments

Safety Measures	Note
Intraocular pressure (IOP)	IOP will be measured on both eyes at Baseline, Month 12, Month 24, and Month 36.
Best-corrected distance visual acuity (BCDVA)	BCDVA will be measured for each eye at Baseline, Month 6 and Month 12 in Period 1 and at Month 18, Month 24, Month 30, and Month 36 in Period 2 using a Snellen chart.
	BCDVA in Snellen scale will be converted to logMAR scale using the following equation and be used in all the BCDVA analyses:
	$LogMAR VA = -log_{10} \left(\frac{Snellen numerator}{Snellen denominator} \right)$
Slit-lamp Biomicroscopy	Slit-lamp biomicroscopy examinations will be performed at Baseline, Month 6 and Month 12 in Period 1 and at Month 18, Month 24, Month 30, and Month 36 in Period 2. Grading of the Meibomian glands, lids, lashes, conjunctiva, tear film debris, anterior chamber and lens will be done on an ordinal scale. Cataract severity will be assessed for phakic eyes only.

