5.2. Handling of Missing Data

No imputation for missing data will be performed on any efficacy and safety endpoints. Unless specified otherwise, descriptive summaries will be based on observed cases.

Completely or partially missing onset and resolution dates for AEs, Concomitant Medications (CM), and Medical History (MH) will be imputed in a conservative fashion as follows:

Incomplete Adverse Event Onset Date

- 1. Year imputation
 - o If *year* is missing (or AE onset date is completely missing), then the onset date will not be imputed.
- 2. Month imputation
 - o If *year* is not missing but *month* is missing, then:

- If *year* = year of first study dose date, then set the *month* and *day* to the day and month of first study dose
- Else if $year \neq year$ of first study dose: set *month* to January

3. Day imputation

- o If day is missing (month and year not missing), then:
 - If year = year and month = month of first study dose, then set day to day of first study dose
 - Else if $year \neq year$ and $month \neq month$ of first study dose, then set day to first day of the month in the year

Incomplete Adverse Event Resolution Date

Do not impute if any resolution date is missing.

If the duration of AE is needed, the following approach may be considered:

- o If year is missing (or AE resolution date is completely missing): do not impute
- o If *year* is not missing but *month* and *day* are missing: impute December 31st for missing *month* and *day*
- o If *year* and *day* are not missing but *month* is missing: impute December for missing *month*
- o If *year* and *month* are not missing but *day* is missing: impute last day of the *month* for missing *day*.

Incomplete CM or MH Onset Date

- 1. If year is missing (or CM/MH onset date is completely missing), do not impute
- 2. If *year* is not missing but *month* and *day* are missing, impute January 1st for missing *month* and *day*
- 3. If year and day are not missing but month is missing, impute January for missing month
- 4. If year and month are not missing but day is missing, impute 01 for missing day

Incomplete CM or MH Resolution Date

- 1. If a resolution date is completely missing, do not impute.
- 2. If year is not missing but month and day are missing, use the last day of the year to impute the missing month and date parts of the resolution date.

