8.2. Analysis of Secondary Efficacy Endpoints

8.2.1. Analysis of Continuous Endpoints

The following secondary efficacy endpoints will be summarized using descriptive statistics such as number of observations (n), mean, standard deviation, median, minimum, and maximum by study period and visit. Also, Period 2 summaries will be done by the randomized treatment.

- CFS score and change from baseline at each visit for Period 1 and Entire Study, and change from Month 12 for each visit in Period 2. Shift tables that show the change from baseline (or Month 12) in CFS score as categorical variable will also be provided.
- Conjunctival fluorescein staining score (nasal, temporal, and total scores separately) and change from baseline at each visit for Period 1 and Entire Study, and change from Month 12 for each visit in Period 2. Shift tables for nasal and temporal conjunctival staining scores will be presented as well.

- SANDE symptoms score and change from baseline at each visit for Period 1 and Entire Study, and change from Month 12 for each visit in Period 2
- Symptoms score (5-point scale) and change from baseline at each visit, for each of the five symptoms assessed for Period 1 and Entire Study, and change from Month 12 for each visit in Period 2
- TBUT and change from baseline at each visit for Period 1 and Entire Study, and change from Month 12 for each visit in Period 2
- Schirmer test and change from baseline at Month 12 visit (Period 1), change from Month 12 visit at Month 24 and Month 36 visits (Period 2), and at each visit (Entire Study)
- Use of Artificial Tears over the last week (the average number of times per day and the number of days the artificial tears were used will be summarized separately) and change from baseline at each visit for Period 1 and Entire Study, and change from Month 12 for each visit in Period 2

In addition to descriptive statistics and shift table, mixed model for repeated measures (MMRM) will be applied to estimate the response of change from Month 12 for the following endpoints;

- CFS, Conjunctival fluorescein staining score, SANDE symptoms score, Symptoms score (5-point scale), TBUT, Schirmer test and Use of Artificial Tears over the last week.

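### A randomised patient with no Month 12 Schirmer value gets the Day 1 pre-treatment value as Period 2 baseline, so that patient's change from Month 12 includes the open-label year

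*SAP*

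**What the plan says.** SAP 4.2.2 takes the Month 12 measurement as the Period 2 baseline. When there is none, "the last observed measurement or derived score prior to the first dose of the Period 2 double-masked study treatment will be used" in its place. No limit is set on how old that value may be.

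SAP 4.2.3 then fixes the Period 2 outcome: "For Period 2 analyses, change from Month 12 will be the change used in the analyses". In SAP 4.1.4 the Period 1 Month 12 window opens at Day 316. The Period 2 Month 12 window has a dash as its lower limit and closes at "1(First Dose Date in Period 2").

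For Schirmer, SAP 8.2.1 plans "Schirmer test and change from baseline at Month 12 visit (Period 1), change from Month 12 visit at Month 24 and Month 36 visits", the latter two being the Period 2 time points. SAP 2.2.2 lists this as a secondary endpoint. SAP 8.2.1 also models it by MMRM, with the Month 12 value as a covariate. For IOP, SAP 4.4.2 states "IOP will be measured on both eyes at Baseline, Month 12, Month 24, and Month 36". A note to SAP Table 1 adds that "Schirmer test and IOP will NOT be performed at Month 18 and 30 visits".

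Entry requires, in the eye that qualifies, "Schirmer test without anaesthesia scored <10 mm/5min in the same eye at Baseline Visit" (Protocol 7.1, criterion 5). On missing data, SAP 5.2 says "No imputation for missing data will be performed on any efficacy and safety endpoints", and Protocol 13.8 says the same for primary and secondary endpoint analyses. SAP 10 does not list the rule in 4.2.2 as a departure from the protocol.

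**The concern.** Carrying a value forward does little harm when a recent one exists. For Schirmer none is planned. The test is absent from the Month 3, 6 and 9 procedures (Protocol 10.1.2) and from the unscheduled-visit procedures (Protocol 10.1.7). The only protocol-specified value before Month 12 is the one taken on Day 1, before any study drug.

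For a patient so imputed, the quantity labelled change from Month 12 is change from before treatment. It contains two things that do not belong to Period 2: whatever happened to Schirmer during the open-label year, and regression to the mean. The second arises because Day 1 values are selected low by the entry limit. They are selected low again when both eyes qualify with equal CFS, since SAP 4.2.1 then takes the eye with the lower Schirmer.

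In the MMRM the same Day 1 value enters twice, in the response and as the covariate labelled Month 12, so the covariate mixes pre-treatment and on-treatment values. In addition, two programmers could produce different Schirmer tables, depending on whether they follow SAP 4.2.2 or SAP 5.2.

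**Working it through.** The plan states no figure on this point, so the check sets the rule against the visit schedule and then sizes the effect.

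**Which value the rule selects when Month 12 is missing**

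- Schirmer: Day 1. Nothing else is scheduled in Period 1, and the test is not an unscheduled-visit procedure.
- IOP: Day 1 by default. IOP is an unscheduled-visit procedure (Protocol 10.1.7; SAP Table 1), so a later Period 1 value may exist and would be used instead.
- DEQS: Month 6, on treatment (note d to SAP Table 1).
- BCDVA and slit lamp: also Month 6, but SAP 9.4 and 9.5 plan only change from baseline for these.

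**Time covered for an affected Schirmer patient** (target days from SAP 4.1.4)

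- Month 24: intended 720 − 360 = 360 days; actual 720 − 1 = 719 days; ratio 719/360 = 2.0.
- Month 36: intended 1080 − 360 = 720 days; actual 1080 − 1 = 1079 days; ratio 1079/720 = 1.5.

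**Shift in an arm's mean change**

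For one affected patient,

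(Month 24 − Day 1) = (Month 24 − Month 12) + (Month 12 − Day 1).

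Let m be the share of analysed patients whose Period 2 baseline is the Day 1 value. Let D be their mean Day 1 to Month 12 change, including regression to the mean. The arm mean then shifts by m × D. The documents give neither quantity, so both ranges below are assumptions (shift in mm).

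| D (mm) | m = 2% | m = 5% | m = 10% | m = 20% |
|---|---|---|---|---|
| 1 | 0.02 | 0.05 | 0.10 | 0.20 |
| 2 | 0.04 | 0.10 | 0.20 | 0.40 |
| 3 | 0.06 | 0.15 | 0.30 | 0.60 |
| 4 | 0.08 | 0.20 | 0.40 | 0.80 |

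**Effect on the comparison of arms**

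This was simulated with 147 and 98 patients, 4,000 runs, D = 2, no true Period 2 change, no treatment effect, and missingness unrelated to arm. The assumed between-patient SD was 2.5 and the within-patient SD 2. The 10 mm entry cut was not modelled, so D stands for the total Period 1 change.

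| m | Mean change, IKERVIS | Mean change, vehicle | Difference, raw | Difference, baseline-adjusted |
|---|---|---|---|---|
| 5% | 0.091 | 0.100 | −0.008 | −0.008 |
| 10% | 0.203 | 0.202 | 0.001 | 0.003 |
| 20% | 0.395 | 0.397 | −0.002 | 0.002 |

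The true change is 0 in both arms, so the within-arm means are spurious and match m × D. The differences are consistent with simulation noise. The SD of a change is √(2² + 2²) = 2.83, the standard error of a difference is 2.83 × √(1/147 + 1/98) = 0.37, and over 4,000 runs the simulation error is 0.37/√4000 = 0.006.

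**The case against.** **The case should be rare.** Only randomised patients have a Period 2 baseline, and randomisation depends on a Month 12 CFS grade read at the slit lamp. Protocol 10.1.3 lists Schirmer before the randomisation step, Protocol 10.1 requires the listed order, and Protocol 11.3 places Schirmer 15 minutes after the staining test. A randomised patient has therefore normally been examined in person at the visit where Schirmer is due. SAP 7.6 mentions remote visits, but in connection with drug returns, and it does not show that Month 12 Schirmer values are missing. This stands: the share is probably small, though a single test can still be skipped.

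**The specific rule governs the general one.** SAP 4.2.2 deals expressly with a reference value taken before the first masked dose, whereas SAP 5.2 speaks of endpoints generally. A reader can guess that 4.2.2 is meant to apply. This stands in part: the intention can be inferred, but 5.2 allows no exception and SAP 10 is silent about Protocol 13.8.

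**IOP is a weaker case.** A reader might infer that IOP is affected in the same way as Schirmer. The documents do not support that. A later unscheduled value may exist, IOP is not in the MMRM, its listed endpoint is change from baseline, and change from Month 12 appears only as an alternative in SAP 9.3.

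**Leaving the baseline missing also costs information.** That is true, and the cost is counted under the fix.

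**Conclusion.** The point holds for Schirmer, as a low-priority correction. With no look-back limit in SAP 4.2.2 and an open-ended window in SAP 4.1.4, a missing Month 12 Schirmer is replaced by a pre-treatment value selected low, and that patient's Period 2 change is mislabelled.

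The size is m × D. At an assumed 5% to 10% imputed and a 2 to 4 mm Period 1 change, it is 0.05 × 2 = 0.1 mm to 0.10 × 4 = 0.4 mm in the arm mean. Neither input is in the documents. Protocol 4.1.1 reports only that Schirmer did not improve relative to vehicle at Month 6 in the pivotal study, which gives no value for D.

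Two stronger readings are not supported. One is that the reported Period 2 mean contains the whole open-label year: that is true of an imputed individual, while the mean moves only by m × D. The other is that the IKERVIS-vehicle comparison is biased: the substituted value predates the first masked dose, and the difference is unbiased in expectation if missingness is unrelated to arm. What is harmed is the within-arm Schirmer change and the meaning of the Month 12 covariate in the Schirmer MMRM. Any loss of precision has not been calculated.

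IOP is affected only when no later unscheduled Period 1 value exists, and only for the change from Month 12 in SAP 9.3. DEQS falls back to an on-treatment Month 6 value, which is stale but not pre-treatment.

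**What to change.** 1. **SAP 4.2.2.** Allow carry-forward of the Period 2 baseline only from values taken between Day 316 and the first masked dose, or from Month 9 onward for measures assessed quarterly. Never use Day 1. Otherwise leave the change from Month 12 missing. For Schirmer this amounts to almost no carry-forward.
2. **SAP 4.1.4.** Give the Period 2 Month 12 window the same lower bound. Express it as Study Day 316 counted from the Period 1 treatment start, because that part of the table is in Period 2 study days. Changing 4.2.2 alone would leave a window that still admits Day 1.
3. **SAP 5.2 and SAP 10.** State the remaining carry-forward as an exception in 5.2, and list it in SAP 10 as a departure from Protocol 13.8.
4. **Reporting.** Give the number of carried-forward Period 2 baselines by endpoint and arm.

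The cost is a few sentences, plus the loss of some patients from the change-from-Month-12 analyses of Schirmer (including its MMRM), IOP and DEQS. At an assumed 5% to 10% missing on one measure, that is 0.05 × 245 ≈ 12 to 0.10 × 245 ≈ 25 patients for that measure. The share is probably smaller for Schirmer, for the reasons given under the objection.
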